10.8. Development Safety Update Reports

The CI will submit (in addition to the expedited reporting above) DSURs once a year throughout the clinical trial, or on request, to the Competent Authority (MHRA in the UK), Ethics Committee, Host NHS Trust and Sponsor.

11. STATISTICS

This section has been written by our statistician.

11.1. Description of Statistical Methods

Descriptive statistics will be used to describe the group demographics and outcomes.

The continuous glucose records will be analysed methodically by the CI, research dietitian and statistician. Data to be obtained include –

- pre-meal BG level
- peak BG level
- peak BG excursion from baseline at 3, 5, 8 and 12 hours following the meal
- time of peak BG level
- time of peak BG excursion
- area under the curve at time-points 0-4 hours, 4-6 hours, 6-8 hours, 8-12 hours post-meal

The relationship between the insulin timing and the mean change in postprandial blood glucose levels will be analysed and described.

Comparisons using paired t tests for normally distributed data, and Mann-Whitney U tests for non-parametric data will be used to examine the differences in areas under the postprandial BG curves and the postprandial BG levels by insulin timing.

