5. OBJECTIVES AND OUTCOME MEASURES

Objectives	Outcome Measures	Timepoint(s) of evaluation of this outcome measure (if applicable)

Primary Objective To determine whether additional insulin boluses for the fat and protein content of a meal given before, one or two hours after a meal optimise post-prandial blood glucose levels in children with Type 1 diabetes using multiple daily
	
Continuous subcutaneous glucose profiles will be examined to determine –
 
 mean post-prandial glucose excursion for 8 hours following the test meal 	
Continuous Glucose Monitoring profiles during the 12 hours following the test meals

[figure not shown]
injections?		

Secondary Objectives
 
To examine other indices of BG control following additional insulin boluses for the fat and protein content of a meal given before, one or two hours after a meal in children with Type 1 diabetes using multiple daily injections?
	
Continuous subcutaneous glucose profiles will be examined to determine –
 
 • peak BG level • peak BG excursion from baseline (pre-meal BG level) • time of peak BG level • timing of peak BG excursion 
area under the curve at time-points 0-3 hours, 3-5 hours, 5-8 hours, 8-12 hours post-meal
	
Continuous Glucose Monitoring profiles during the 12 hours following the test meals

Tertiary Objectives
 
1. To assess the acceptability of giving additional insulin doses for fat and protein to children using MDI
 
2. To assess the safety of giving additional insulin doses for fat and protein to children using MDI
	
1. Questionnaires to parents and children during and at the end of the study
 
2. All episodes of hypoglycaemia (BG less than 4 mmol/l) or hyperglycaemia (BG >12 mmol/l) either on CGM or self-monitoring of BG
	
Collection of data during and at the end of the study

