6. TRIAL DESIGN

6.1. Summary –

The study design is a repeated measures study involving the provision of a standard high protein/high fat evening test meal on 3 different evenings within a 7-day period in the same study subject. The children/adolescents will be instructed to give an insulin dose for the carbohydrate before the meal (calculated using their optimal insulin to carbohydrate ratio (ICR)). In addition they will have an extra dose for the fat and protein content either before (together with the dose for the carbohydrate in the meal [control meal]), 1 hour after, or 2 hours after the first insulin dose given before the meal. These will be carried out in a random order in each subject. Glucose monitoring will be carried out using CGM for the whole 7 day period.

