On three evenings over the next 7 days, the children will eat a standard high protein/high fat meal. The evenings will not be set, but will depend on the child and family schedule. The study meal will not be eaten on the evening that the CGM is inserted as sensor accuracy takes 24 hours to maximise accuracy. The child and family will be able to choose which days during the study period on which they complete the study meals but will be advised to avoid days when the participant has undertaken lots of exercise, is hypoglycaemic immediately before the meal or has had frequent hypoglycaemic episodes, or has been unwell.

The standard meal will be a portion controlled gluten-free meal provided and delivered by Wiltshire Farm Foods consisting of a meat-based main course and dessert. These will be kept frozen until used by participants and prepared according to manufacturer instructions. These meals come in two sizes which allow portion sizes to be adjusted for different ages of child, but the proportions of fat, protein and carbohydrate will be kept constant for each child, and by definition the meals will be high in protein and high in fat.

Insulin doses with the standard meal will be given according to calculations carried out by the dietitian and administered in one of three ways.

The three evenings in random order will be as follows -

1. Insulin units based on ICR and fat/protein dose given together immediately before the meal [control meal].
2. Insulin units based on ICR given immediately before the meal plus extra insulin for fat/protein units given 1 hour after the first meal dose.
3. Insulin units based on ICR given immediately before the meal plus extra insulin for fat/protein units given 2 hours after the first meal dose.

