11.2. The Number of Participants

We estimate that using a three-treatment, three period cross-over design, 36 people will achieve 80% power to detect a 2 mmol/L difference in mean 5 hour postprandial glucose excursion at the 5% significance level. Although we do not anticipate any losses to follow-up or withdrawals due to side-effects from the study we will aim to recruit 40 to ensure power is maintained if this does arise. This power calculation has been carried out by our study statistician.

In order to allow for drop-outs, we have made the decision to recruit 40 patients.

Previous intervention studies of fat/protein interventions in children using insulin pumps have used 24-42 patients with significant differences in BG levels at the 0.04 and 0.03 levels of significance (5-8).

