11.3. The Level of Statistical Significance

$P < 0.05$ will be used to demonstrate statistical significance.

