11.6. Inclusion in Analysis

All data available from all participants will be used for the analyses. If a child has become hypoglycaemic (BG $< 4.0 \text{ mmol/l}$) during the profile period then subsequent data will be analysed separately. If any child has had to treat a high BG level with additional insulin (except for a correction dose at the evening meal), then subsequent profile data will be analysed separately. However in either instance, the data up to the event will be included in all analyses. The two other meals would still be eligible for the study analyses if there were no similar events.

If there have been any protocol breaches, such as further food during the evening after the main meal, then all the subsequent data will not be used in the analysis for that meal. Education of the participants and parents will be vital to ensure that such eventualities are rare.

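### Non-normal outcomes get an independent-groups test although every child eats all three meals, and no primary contrast or error control is named for the three timings

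*Combined protocol and SAP*

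**What the plan says.** **Design.** Section 6.1 describes a repeated measures study with three dosing schedules per child: "These will be carried out in a random order in each subject". Section 11.2 bases the sample size on "using a three-treatment, three period cross-over design". Section 6.3 lists the schedules and labels the first as the reference: "Insulin units based on ICR and fat/protein dose given together immediately before the meal [control meal".

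**Tests.** Section 11.1 says: "Comparisons using paired t tests for normally distributed data, and Mann-Whitney U tests for non-parametric data will be used". The sentence applies these tests to areas under the curve and to glucose levels, by timing. The sentence before it names no test: "The relationship between the insulin timing and the mean change in postprandial blood glucose levels will be analysed and described".

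**Primary outcome.** Section 5 and the synopsis give it as "mean post-prandial glucose excursion for 8 hours following the test meal".

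**Error control.** Section 11.3 says only that P<0.05 "will be used to demonstrate statistical significance". Section 11.2 does not say which two timings its 2 mmol/L difference separates.

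**Incomplete children.** After hypoglycaemia or an extra correction dose at one meal, section 11.6 says: "The two other meals would still be eligible for the study analyses if there were no similar events". Section 11.5 plans a complete-case analysis, with multiple imputation as sensitivity.

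**The concern.** Two separate matters.

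1. Mann-Whitney U treats the two sets of results as coming from different children. Its standard error therefore includes the between-child variation that the cross-over is meant to remove. The section never mentions a signed-rank, Friedman or mixed-model analysis that would correct this. It also leaves open whether normality is judged on within-child differences or on raw values, which decides how often the unpaired test is used, and whether the test sentence governs the primary outcome at all.

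2. Three timings give three pairs, or two comparisons against the control meal. With no primary contrast and only P<0.05, a claim that one timing is best can rest on whichever test crosses the line.

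**Working it through.** **Inputs from the documents.** 36 children, 80% power, 2 mmol/L, 5% level (section 11.2); three timings per child (section 6.3). **Not in the documents:** SD, within-child correlation, shape of the data, sidedness and the normality rule. These are assumed below.

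**Step 1: the plan's own figure.** With no SD stated, 36 cannot be reproduced, only inverted. For one two-sided paired contrast, the normal approximation gives SD of differences = 2 × √36 / (1.960 + 0.842) = 12 / 2.802 = 4.28 mmol/L. The exact paired t (noncentral t, 35 df) gives 4.16, a within-child SD of 4.16/√2 = 2.94. Section 11.2 uses the 5-hour excursion and the primary outcome is 8-hour, so 4.16 is only a working value for the primary.

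**Step 2: Mann-Whitney alone, no true difference.** Simulated type I error at correlations 0.3 / 0.5 / 0.7 is about 2% / 0.7% / 0.1%, for normal and skewed data alike.

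**Step 3: the whole two-branch rule.** The paired t test is used unless Shapiro-Wilk rejects normality at 5%; otherwise Mann-Whitney is used. The comparator is the same rule with signed-rank in the second branch. Settings: n=36, shift 2 mmol/L, data scaled to SD of differences 4.16, 6,000 replicates per cell, lognormal skew with sigma 0.5 (moderate) or 0.9 (strong), correlation on the latent scale.

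| Data | Normality judged on | Plan, power % at 0.3 / 0.5 / 0.7 | With signed-rank |
|---|---|---|---|
| Normal | differences | 79.3 / 77.2 / 77.3 | 79.9 / 78.7 / 80.0 |
| Normal | raw values | 78.9 / 75.9 / 75.4 | 79.7 / 78.6 / 79.8 |
| Moderate skew | differences | 84.3 / 82.1 / 73.0 | 84.5 / 86.0 / 86.9 |
| Moderate skew | raw values | 87.1 / 78.7 / 55.9 | 86.6 / 87.8 / 88.5 |
| Strong skew | differences | 98.9 / 98.9 / 97.8 | 97.0 / 97.6 / 98.0 |
| Strong skew | raw values | 99.6 / 99.3 / 97.7 | 97.4 / 97.8 / 98.2 |

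Under moderate skew the losses at correlations 0.5 and 0.7 are:
- judged on differences: 86.0 − 82.1 = 3.9 and 86.9 − 73.0 = 13.9 points;
- judged on raw values: 87.8 − 78.7 = 9.1 and 88.5 − 55.9 = 32.6 points.

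At correlation 0.3 there is no material loss.

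**Step 4: several contrasts at 5% each.** If the tests were independent, the chance of at least one false positive would be 1 − 0.95² = 9.75% for two and 1 − 0.95³ = 14.3% for three. Paired t tests that share children and meals are correlated; simulation (n=36, normal data, equal correlations) gives about 9% and 12%.

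**Step 5: testing timing overall first.** With a 2-df F test as gate, family-wise error is about 5.1% when the three timings have similar variances and about 6% when one has twice the SD of the others. Power for a 2 mmol/L contrast after the gate depends on what section 11.2 sized:
- One unadjusted contrast (SD 4.16): 70% at n=36 if the third timing lies midway and 76% if it equals one of the other two; 75% and 81% if all 40 complete.
- The 2-df test itself: that test keeps its 80%. Contrast power at n=36 is 79% for equally spaced timings (SD 3.78), or about 71% if only one timing differs (SD 4.37; about 77% at n=40).

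These gate figures are for normal data only.

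**The case against.** The strongest reply is that the practical harm of the first matter is narrow. The largest loss needs moderate skew, correlation 0.7 and normality judged on raw values all at once. Judged on differences, the usual reading beside a paired t test, the loss is 4 to 14 points. Lognormal data are a rough stand-in for an excursion from baseline, which can be negative. All of that stands, and it limits the size of the point; it does not make an independent-groups test right for paired data.

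It is also fair to say that glucose levels compared by timing can reasonably be read to include the mean excursion, so doubt over the primary outcome is a matter of clarity. On the second matter, there is one primary outcome and a labelled control meal, and formal adjustment in a 40-child study is partly a matter of preference. Naming the contrast is not.

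Three stronger readings are tempting, and the documents support none of them:
- That the wrong test produces false positives. In the settings tried it does the reverse. The low error rates in step 2 belong to Mann-Whitney alone; under moderate skew, judged on differences, the two-branch rule as a whole has about 3.6%, 3.8% and 2.4%.
- That the trial's power collapses. Mann-Whitney used on normal data at correlation 0.7 has about 23% power, but the plan sends normal data to the paired t test.
- That 36 is too few. Section 11.2 gives neither an SD nor a contrast, so this cannot be shown.

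**Conclusion.** The point holds in two parts. Mann-Whitney U is the wrong test for this design as written, and nothing elsewhere in the protocol corrects it. Its cost is possible lost power in the non-normal branch: about 4 to 14 points (normality judged on differences) or 9 to 33 (raw values) under moderate skew at correlation 0.5 to 0.7, and little otherwise. These sizes depend on the assumed SD, skew, correlation and normality rule.

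The missing primary contrast and error control can be verified from the text alone. The family-wise error of about 9% or 12% depends on how many pairs are tested; the control-meal label suggests two, but the plan does not say so. This should be fixed before the data are analysed. It does not call the design or the sample size into question.

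**What to change.** **Section 11.1.** Replace Mann-Whitney U with Wilcoxon signed-rank on within-child differences. State that normality is judged on those differences, and that this paired analysis applies to the primary 8-hour mean excursion.

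**Sections 11.1 and 11.3.** Choose one of the following:
- Name one primary contrast, tested at 5%. This needs no alpha adjustment and leaves the 36 of section 11.2 unchanged. Label the other contrasts secondary.
- Test timing overall first (2-df test for normal outcomes, Friedman for non-normal ones) and test pairs only if it is significant. Describe the error control as about 5% under similar variances, not as exact.

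A mixed model with timing and period as fixed effects and child as random could supply the 2-df test and would keep children with one affected meal, as section 11.6 intends. It is optional. If used, it must be reconciled with the complete-case rule in section 11.5.

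**Cost.** Wording only; no change to design or visits. Signed-rank gives up at most about 2 points of power under strong skew with low correlation (for example 99.6% to 97.4%). The overall-test route lowers contrast power from 80% to about 70 to 76% at n=36 if section 11.2 sized a single unadjusted contrast; the named-contrast route avoids that loss.

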8.3. Randomisation, blinding and code-breaking

Randomisation is required only for the order of the insulin dosing. The study statistician will provide the randomisation codes and the study dietitian will make up sealed envelopes with all the instructions inside for the schedule for the participant according to the randomised order of treatment. This schedule will form part of the study diary for each participant. The envelopes will be kept in the research office in Oxford until they are needed, when the next one will be taken for the next participant entering the study at any of the participating sites. The envelope will be opened by the research nurse or dietitian at the first study visit when the CGM is being inserted. As the same research team will be working at all sites there is no requirement for separate codes for each site.

Unblinding will not be required as this is not a blinded study. Participants and researchers will know the order of the insulin doses for the test meal from the start of the study.

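### The three randomised insulin timings are compared with two-condition tests that have no meal-position (period) term, so any trend from first to third meal adds to the error and any imbalance in the orders stays uncorrected

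*Combined protocol and SAP*

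**What the plan says.** Section 6.1 and Section 6.3 give every child all three timings of the fat/protein dose on three evenings, in random order. Section 8.3 confirms that "Randomisation is required only for the order of the insulin dosing" and does not say whether the six possible orders are balanced.

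Section 11.2 sizes the trial as a "three-treatment, three period cross-over design" and states that "36 people will achieve 80% power to detect a 2 mmol/L difference in mean 5 hour postprandial glucose excursion" "at the 5% significance level". It gives no SD. The target is 40 children, to protect power against losses.

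Section 11.1 names two inferential methods: "Comparisons using paired t tests for normally distributed data" and Mann-Whitney U tests for data that are not normal. Both compare two conditions. No section names a period, meal-position or sequence term, a mixed model or a repeated-measures ANOVA. Section 6.1 uses the label repeated measures, and Section 11.1 promises to describe how glucose change relates to timing, but neither specifies a model.

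**The concern.** A child's three meals fall at different points of the sensor week. If the outcome moves with meal position, the difference between two timings in one child contains the timing effect plus the shift between the two positions. A paired t test cannot separate these. With equally used orders the shift averages out of the mean difference but stays in its variance, so intervals widen and power falls. With unequal orders, part of the shift also stays in the mean difference of the trial actually run.

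Unequal orders are likely: 40 is not a multiple of six, and meals can be lost, excluded or cut short under Sections 8.7, 9.3 and 11.6. Some drift is conceivable. The sensor ages, families see live readings because Section 6.3 rejected a blinded monitor, and they gain experience of the test evenings. At stake is precision in the trial's main comparison, in a design whose structure allows the loss to be avoided.

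**Working it through.** **Inputs.** From Section 11.2: n = 36, power 80%, difference δ = 2 mmol/L, 5% level (taken as two-sided). Not in the documents and therefore solved for or assumed: the SD of paired differences σ and the drift g in mmol/L per successive meal.

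**1. The plan's own figure.** Without an SD, n = 36 cannot be reproduced, only solved backwards. For a paired t test with 35 df (critical value 2.030), the noncentrality is δ√n/σ = 2 × 6/σ. Power of 80% requires σ = 4.165 mmol/L, a within-child SD of 4.165/√2 = 2.94. Other conventions give 4.22 (crossover error, 68 df), 4.28 (normal approximation, two-sided), 4.83 (normal, one-sided), 4.73 (two-sided 10%) and 3.56 (5%/3).

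**2. Effect of a linear drift on the paired test.** Over the six orders, two given timings are one position apart in four orders and two apart in two, with signs that cancel. The mean squared gap is (4 × 1 + 2 × 4)/6 = 2. With equally used orders the variance of a paired difference becomes σ² + 2g², with σ² = 4.165² = 17.34. For g = 1 this is 19.34, so the SD is 4.398 and the interval widens by 4.398/4.165 = 1.056.

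| Drift per meal (assumed) | SD of difference | Interval width | Power, n = 36 | Power, n = 40 |
|---|---|---|---|---|
| 0 | 4.165 | 1.00 | 80.0% | 84.2% |
| 0.5 | 4.224 | 1.01 | 78.9% | 83.1% |
| 1.0 | 4.398 | 1.06 | 75.6% | 80.1% |
| 1.5 | 4.674 | 1.12 | 70.4% | 75.2% |
| 2.0 | 5.034 | 1.21 | 64.0% | 68.8% |

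**3. If the SD is smaller.** At g = 1, σ = 3 gives √(9 + 2)/3 = 1.11 and σ = 2 gives √(4 + 2)/2 = 1.22, so the interval widens by 11% to 22%.

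**4. Model with child, meal position and timing.** Residual df are 36 × 2 − 2 − 2 = 68. With balanced orders and σ = 4.165, power is 81.1% whatever the drift. Simulation (4,000 runs per setting, n = 36) agrees:

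- Balanced orders, drift 0, 1, 2: paired t 80%, 77%, 66%; period model 81%, 81%, 80%.
- Orders drawn without balancing, same drifts: paired t 80%, 75%, 64%; period model 79%, 80%, 80%.
- No true difference, balanced orders, drift 2: the paired t test rejects in 1.8% of runs and the period model in 5.5%. The paired test is conservative there, not anti-conservative.

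**5. Imbalance in the realised trial.** With unbalanced random orders, the SD of the estimated timing difference is 0.73 without and 0.71 with the period term at drift 1, and 0.83 against 0.70 at drift 2. The excess is drift left in the estimate.

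**6. Price of the term when there is no drift.** With balanced orders, residual df fall from 70 to 68, which raises the critical value by about 0.05%. With orders drawn without any balancing, the simulated SD of the estimate is 0.696 against 0.687, a ratio of 1.013.

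**The case against.** The best case for leaving Section 11.1 alone has four parts.

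- **Validity is not at risk.** Order is randomised within each child, so the paired contrast is unbiased on average, and with balanced orders drift makes the test conservative. This stands. The point concerns precision only; a reader might infer bias or inflated false positives, and neither follows.
- **Little drift may exist.** Section 6.3 already keeps test meals off the insertion evening, the run-in week settles the carbohydrate ratio, and Section 8.5 fixes doses and instructions in advance. If the excursion is taken from the pre-meal value, a constant sensor offset cancels. This also stands: no document shows a trend or its size. At 0.5 mmol/L per meal the loss is about one point of power. The 64.0% case needs a first-to-third shift of 4 mmol/L, twice the target difference, and should not be read as a forecast.
- **Paired tests are compatible with a crossover.** A reader might infer that Section 11.1 contradicts the power statement. It does not: Section 11.2 names a design, not a model, an error term or an SD. With 35 df and an SD of 4.16, the paired test has exactly the stated power.
- **Balance may already be arranged.** Section 8.3 leaves code generation to the statistician without giving the method, so blocking is possible. Lost or excluded meals could still upset it.

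What remains is an uneven trade: a small, nearly fixed price against a loss of unknown size.

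**Conclusion.** The point holds as one of efficiency and of completeness in the analysis plan. Section 11.1 has no meal-position term, although the order is randomised over three meals. At the back-solved SD of 4.16 mmol/L and n = 36, the plausible-looking range of 0.5 to 1.0 mmol/L per meal costs about 1 to 4 points of power and 1% to 6% in interval width. The relative widening is greater if the SD is smaller, but power at 36 children then stays high (94% at an SD of 3 and drift of 1.0).

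These figures assume a linear drift, equally used orders, a two-sided 5% test and an SD inferred from the sample-size statement. That SD belongs to the 5-hour excursion, whereas the primary outcome covers 8 hours. If it came from earlier paired data it may already include some drift, and the loss would then be overstated.

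A reader might also infer that 36 is the wrong number. The documents do not support that: without a stated SD it can be neither confirmed nor refuted.

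**What to change.** In Section 11.1, make the primary analysis one linear mixed model on all available meals, with child as random effect and timing (three levels) and meal position (1, 2, 3) as fixed effects. Report the pairwise timing differences with confidence intervals from that model. Define position as the order in which the analysed meals were eaten, since abandoned evenings can be repeated, and report how many children followed each order.

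The cost is two degrees of freedom: well under 1% in interval width if the orders are close to balanced, and about 1% if they were drawn without balancing. No new data are needed, because the randomised schedule is part of each child's diary (Section 8.3). A random intercept alone assumes the same variance for all three pairwise differences, which separate paired tests do not; an unstructured within-child covariance relaxes this.

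The order codes need not be regenerated. Section 8.3 does not show them to be unbalanced, and Appendix B indicates that participants had already been enrolled when the protocol was amended.

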2. SYNOPSIS

Trial Title	Investigation of Appropriate Timing of Additional Insulin Dosing for Fat and Protein in Children with Type 1 Diabetes using Multiple Daily Injections	
Internal ref. no. (or short title)	Fat/Protein Study	
Clinical Phase	Phase 4	
Trial Design	Controlled observational study	
Trial Participants	Children aged 6 to under 18 years of age with type 1 diabetes (T1DM)	
Planned Sample Size	40	
Treatment duration	1 week	
Follow up duration	No follow-up at the end of the trial period	
Planned Trial Period	1 year	
	Objectives	Outcome Measures
Primary	To determine whether additional insulin boluses for the fat and protein content of a meal given before, one or two hours after a meal optimise post-prandial blood glucose levels in children with Type 1 diabetes using multiple daily injections?	Continuous subcutaneous glucose profiles will be examined to determine – 
 • mean post-prandial glucose excursion for 8 hours following the test meal
Secondary	To examine other indices of BG control following additional insulin boluses for the fat and protein content of a meal given before, one or two hours after a meal in children with Type 1 diabetes using multiple daily injections?	Continuous subcutaneous glucose profiles will be examined to determine – 
 • peak BG level • peak BG excursion from baseline (pre-meal BG level) • time of peak BG level from baseline measurement • Rate of BG excursion from baseline to peak • mean post-prandial glucose excursion for 5 and 12 hours following the test meal • area under the curve at time-points 0-3 hours, 3-5 hours, 5-8 hours, 8-12 hours post-meal • Time from baseline BG at which BG returns to baseline level
Investigational Medicinal Product(s)	Insulin	
Formulation, Dose, Route of Administration	Insulin Aspart (NovoRapid) given in a dose according to the protocol, subcutaneously	

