At the end of the run-in week, participants will then attend the outpatient clinic or day care ward research facility at the Oxford Children's Hospital or the Horton Hospital outpatient clinic in Banbury or the Royal Berkshire Hospital in Reading (Visit 2). At this visit, the subcutaneous glucose sensor will be inserted by the research nurse and children and young people and their families will be trained on its use prior to the study commencing. CGM records BG levels every 5 minutes over 7 days and thus provides much more information than routine BG testing. These systems are regularly used by the Paediatric Diabetes team in clinical care and are well accepted by patients. The CGM records will enable researchers to calculate the area under the curve for post-prandial BG response to determine if there are significant differences between the test insulin dosing schedules. Children and young people will also record their BG levels from routine finger pricks, pre-prandially and before bed and on waking in the morning.

We considered using a blinded CGM system which does not reveal current blood glucose levels in order to reduce participant and parental anxiety, however the only system like this on the market does not alarm on hypoglycaemia which is an essential safety measure for this study and this option was therefore rejected.

Also at Visit 2, the study dietitian will review BG readings and food diary from the previous week and optimise ICR doses of rapid acting insulin. This ratio will then be used to calculate insulin doses for the study meals according to the following algorithm based on the Pankowska (Warsaw) equation [6] and recommendations from the latest systemic review of current research [9]

Insulin dose for carbohydrate = g CHO x ICR

Insulin dose for fat and protein = FPU x (0.3 x ICR)

TOTAL Insulin dose = (g carbs x ICR) + (FPU x (0.3 x ICR))

Where FPU = fat-protein unit and 1 FPU = 100kcal from fat and protein

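### Section 11 does not make the 8-hour mean excursion the deciding result; it directs tests at four AUC windows, with conflicting cut points, under one unrestricted P<0.05 rule

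*Combined protocol and SAP*

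**What the plan says.** - **Primary outcome.** The synopsis and Section 5 name one: "mean post-prandial glucose excursion for 8 hours following the test meal".
- **Secondary outcomes.** The synopsis lists eleven: peak level, peak excursion, time of peak, rate of rise, mean excursion over 5 h and over 12 h, time to return to baseline, and four AUC windows ("area under the curve at time-points 0-3 hours, 3-5 hours, 5-8 hours, 8-12 hours post-meal"). Section 5 gives the same windows but a shorter list of eight outcomes.
- **Section 11.1.** The data list has no mean excursion over 8 hours or any other period. Its AUC windows are 0-4, 4-6, 6-8 and 8-12 h. Paired t tests or Mann-Whitney tests "will be used to examine the differences in areas under the postprandial BG curves and the postprandial BG levels by insulin timing". A separate sentence has the relation between timing and mean change in glucose analysed and described, with no time horizon and no test.
- **Section 6.3.** The CGM records are to let researchers "calculate the area under the curve for post-prandial BG response to determine if there are significant differences between the test insulin dosing schedules".
- **Section 11.3.** P<0.05 "will be used to demonstrate statistical significance". This is the whole rule.
- **Section 11.2.** The sample size statement is that "36 people will achieve 80% power to detect a 2 mmol/L difference in mean 5 hour postprandial glucose excursion at the 5% significance level".

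No section gives a multiplicity adjustment, an order of testing among secondary outcomes, or a rule for which result settles the comparison of timings.

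**The concern.** The trial asks which of three injection timings gives the best postprandial glucose, so the plan should say which result answers that. The front of the protocol does; the statistics section does not. Someone working from Section 11 alone would test AUC windows and glucose levels, call any P below 0.05 a demonstrated difference, and never be told that the 8-hour mean excursion outranks the rest.

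At stake is a claim that one timing is better resting on a single AUC window while the primary outcome shows nothing. Two sets of windows add a further choice. They share only 8-12 h, so 4 + 4 - 1 = 7 distinct windows are available to an analyst who has seen the data. The study is open-label (Section 8.3), so prior specification is one of the few protections against selective emphasis.

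**Working it through.** **1. The plan's own figure.** Section 11.2 gives 36 children, 80% power and 2 mmol/L, but no standard deviation, so 36 cannot be reproduced. Back-solving n = ((z_alpha + z_power) × SD_diff / delta)² with two-sided 5% gives

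SD_diff = 2 × √36 / (1.960 + 0.842) = 4.28 mmol/L,

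or 4.16 mmol/L with the t distribution on 35 df. This SD is implied, not stated. It does not affect the false-positive rates in steps 2 and 3, which are scale-free; it enters only step 4.

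**2. Four windows, one pair of timings, no true effect.** If the windows were independent:

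1 - (1 - 0.05)⁴ = 1 - 0.8145 = 0.185.

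**3. Allowing for correlation and for three pairs.** The documents give no correlation between windows, so it was varied. The simulation used 36 children, three timings, four outcomes with equal correlation, no timing effect, two-sided paired t tests at 0.05 and 20,000 runs. Sidedness is not stated in the plan; two-sided is assumed. The chance of at least one significant window is:

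| Between-window correlation | One pair | Three pairs |
|---|---|---|
| 0 | 18.8% | 40.9% |
| 0.3 | 17.3% | 38.8% |
| 0.5 | 16.4% | 35.8% |
| 0.7 | 13.2% | 29.8% |
| 0.9 | 9.6% | 22.1% |

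The 18.8% agrees with the exact 18.5% within simulation error. Against the stated 5%, one pair gives about 2 to 4 times the rate, and three pairs about 4 to 8 times (22.1/5 = 4.4; 40.9/5 = 8.2).

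**4. What an adjusted AUC claim would involve.** Four windows by three pairs is 12 tests, so the first Holm threshold is 0.05/12 = 0.0042. Bonferroni at that level gave a simulated family-wise rate of 4.6% at correlation 0 and 2.7% at 0.9. If a window had the same standardised effect as the planned one (2/4.16), power at n = 36 would fall from 80% to about 44% at that threshold. Holm is never less powerful than Bonferroni, so 44% is the floor for a given comparison.

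**5. Window sets side by side.** Synopsis and Section 5: 0-3, 3-5, 5-8, 8-12 h. Section 11.1: 0-4, 4-6, 6-8, 8-12 h. In both sets the first three windows add up to 0-8 h, so an 8-hour AUC can be recovered from either. Section 11.1 nowhere says that this sum is formed or tested.

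**The case against.** The strongest reply is that the plan does name a single primary outcome, and that calling the others secondary already signals their supporting role. The sentence in 6.3 describes what CGM data make possible, mentions no windows and sets no decision rule. A mean excursion over 8 hours is essentially the 0-8 h AUC divided by 8, less the baseline, so 6.3 can be read as compatible with the primary. This has force: 6.3 alone does not show that a window decides the trial. It does not remove the gap, because 11.1 splits the AUC, leaves out the 8-hour summary, and is followed by a significance rule with no restriction.

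Three stronger readings are tempting, and the documents do not support them.

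- *A reader might infer that all eleven secondary outcomes are each tested at 0.05.* In the same simulation that would give about 31% for one pair and 60% for three pairs at correlation 0.5. But 11.1 names tests only for AUCs and glucose levels, and none for time of peak, rate of rise or time to return to baseline. The count of eleven is also the synopsis's; Section 5 lists eight.
- *A reader might infer that the plan has no hierarchy at all.* The synopsis separates primary from secondary outcomes, and Section 5 adds tertiary objectives. What is missing is that distinction in Section 11 and any order among the secondary outcomes.
- *A reader might infer that opposite results in early and late windows would be chance findings.* Moving the same dose later could genuinely raise early glucose and lower later glucose. Multiplicity control would not remove such a conflict; a stated deciding outcome would say which result answers the question.

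Independence between windows is also unlikely within one glucose trace, so the upper ends of the ranges are limits rather than expectations.

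**Conclusion.** The concern holds in this limited form: the analysis section does not follow the named primary outcome, and its rule allows an isolated AUC window to be reported as a demonstrated timing difference. The size is about 10-19% for one pair of timings and 22-41% for all three, against a nominal 5%. These figures assume 36 analysed children, two-sided paired t tests, no true effect, and an equal between-window correlation somewhere from 0.9 to 0. They would be higher if further secondary outcomes were also tested, or if the window set were chosen after seeing the data; neither is quantified here. The plan should be changed, but the fault is one of specification and does not affect the design or data collection.

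**What to change.** - **11.1:** add the 8-hour mean excursion to the data list, name its test, and say which timing pairs it is tested on.
- **11.1 and 11.3:** state that this outcome alone supports a claim that one timing is better. Report every secondary outcome, including each AUC window, as a supportive estimate with a 95% confidence interval and no claim of demonstrated significance.
- **6.3:** reword so that the 8-hour mean excursion determines whether the schedules differ.
- **Synopsis, Section 5 and 11.1:** use one set of AUC windows, fixed before data are seen.
- **If a formal AUC claim is wanted:** test it only after the primary is significant, with Holm adjustment over all windows and timing pairs tested.

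The cost is mainly wording, with no new measurements. Isolated secondary P values below 0.05 can no longer be claimed as demonstrated differences. One cost goes beyond these edits: 11.2 states power for the 5-hour excursion, a secondary outcome in the synopsis. It must be reconciled with the 8-hour primary, with the assumed standard deviation stated, because the documents do not show what power 36 or 40 children give for the outcome that would carry the conclusion.
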